1.5.2. Pregnancy

Risks from the study vaccines to human fetuses are unknown at this time. As such, pregnant females will be excluded from participation, and female subjects of childbearing age will be required to use contraception during this study and for a period after vaccination.

Given the theoretical risk of shedding and transmission to a female partner of childbearing potential, male subjects will also be required to utilize effective contraception precautions for the same period of time.

Each pregnancy should be reported *immediately* (within 48 hours of identification) by email or fax to the Sponsor's safety office and the IRB. Subjects, or their partners, who become pregnant after day 1 will be followed to term. Any SAE experienced during pregnancy must be reported on the SAE report form.

In the absence of any pregnancy complications that meet the criteria of an SAE, a pregnancy should not be reported as an AE.

1.5.3. Lactation

Risks from the study vaccine to nursing infants are unknown at this time. As such, lactating females will be excluded from participation.

1.5.4. Venipuncture

Some discomfort from the needle stick for the blood draw is possible, including swelling or bruising, and there is a very small risk of infection at the site of the needle stick. A few subjects may feel lightheaded and may develop a rapid heartbeat during blood collection. These symptoms can be stopped by having the subject lie down and/or by stopping the procedure.

1.5.5. Allergic Reaction

As with any IP, there is the potential risk of a serious or even life-threatening allergic reaction to one or more components of the IP to be used in this study. The vaccine contains the virus and recombinant (yeast derived) human albumin in a buffer and is considered to have a low risk of eliciting allergic reactions. To further mitigate this risk, subjects with a history of severe allergic reaction of any kind, or significant allergic reaction to a known component of the experimental product, will be excluded from participation. Subjects will be observed for at least 60 minutes (\geq 60 minutes and \leq 90 minutes) after vaccine administration for any signs or symptoms of local and/or systemic intolerance to the study product. Vital signs will be checked within the same observational timeframe (\geq 60 minutes and \leq 90 minutes) after vaccination.

In the event of a severe allergic reaction, the study site is staffed with trained medical personnel and stocked with appropriate medical emergency equipment to provide acute care for conditions such as anaphylaxis. Further, if required, a formal emergency medical response service (rescue

squad, fire department, etc.), capable of treating and transferring any life-threatening injuries to a higher level of medical care, is available in close proximity to the trial site.

1.5.6. Skin Biopsy

In the event that a punch biopsy is indicated, there is a risk of local bleeding and bruising, pain, infection, allergic reaction to the anesthetic, or damage to the structures beneath the skin site such as an artery or a nerve. A separate consent would be used for this procedure.

1.5.7. Arthrocentesis

In the event that an arthrocentesis is indicated, in addition to the risk of pain and hemorrhage, there is a rare (1:2000) risk of introgenic septic arthritis (29). A separate consent would be used for this procedure.

1.5.8. Guillain-Barré Syndrome (GBS)

GBS, an auto-immune disorder of peripheral nerves, has been observed to be temporally related to administration of certain vaccines. There is a background incidence of GBS in North America and Europe of 0.62 to 2.66 per 100,000, with rates higher with advancing age and in males vs. females (30). Additionally, recent epidemiologic data from the Centers for Disease Control and Prevention indicate that there is no statistically significant increased risk of GBS in the 6 weeks following vaccination with licensed vaccines (31). Overall, the chance of developing GBS is very unlikely but it is possible. In rare situations when GBS does occur, approximately 85% of GBS patients make a complete or nearly complete recovery. Management includes supportive care, plasmapheresis, and administration of high dose IgGs. The death rate from GBS may be 3% to 7% (32).

To mitigate this risk, individuals with a history of GBS, other neurologic diseases per the Principal Investigator's (PI) discretion, or other significant reaction to vaccination will be excluded from participation.

1.5.9. Unknown Risks

As with all research of new vaccines, there is a remote possibility of risks that are unknown or that cannot be foreseen based on available information. This would include late effects that have been seen with some vaccines.

1.5.9.1. Shedding of Virus

There is a theoretical risk of shedding of vaccine virus and transmission to contacts. The finding of low levels of viral RNA in salivary gland, kidney, and nasal turbinates until day 15 in the NHP biodistribution study (Section 1.1.3) indicates the possibility of shedding of the vaccine virus in a clinical setting, and the potential for transmission, as reported for the preceding rVSV-ZEBOV-GP vaccine (33). Participants in this study are advised to take measures to limit contact spread of the vaccine virus to other persons or susceptible animals.

1.5.10. Alternatives to this IND Product or Study

At this time, there is no FDA-approved or European Medicines Agency-approved product that affords protection against infection with Marburg. PHV01 is one of five vaccines in development intended to protect against Marburg (34). Subjects may choose not to participate in this study.

1.5.11. Intended Benefit for Subject

There is no intended direct benefit for study subjects. It is possible that vaccination with PHV01 may result in an immune response to Marburg. The protective efficacy of such responses is unknown. The results of this study may be of benefit to humanity in the future.

1.5.12. Risks to the Study Personnel and the Environment

The principal risk for study personnel is exposure during dose preparation. In the clinical setting there is a risk of exposure to infectious pathogens from study subjects through an accidental needlestick during dosing with the live attenuated PHV01 vaccine, or to blood-borne pathogens. There is also the theoretical risk of transmission through contact exposure to blood or body fluids after dosing. Adherence to good hygiene practices and standard operating procedures (SOPs) for working with infectious agents and universal precautions will reduce the risk of exposure.

There are no known risks to the environment other than those associated with the generation of biohazardous waste attendant to vaccination of humans. All biohazardous waste will be disposed of as stipulated by local, state, and federal regulations and in accordance with study site SOPs. The environmental risk of PHV01 to livestock is thought to be very low due to the attenuation of the WT VSV by deletion of the G protein, which is a virulence factor.

1.6. ROUTE OF ADMINISTRATION, DOSAGE REGIMEN, TREATMENT PERIOD

PHV01 or placebo will be administered once to each subject by IM injection. Subjects will be enrolled into treatment groups and randomized to either study product or placebo.

Detailed instructions for preparation of IP are provided in a separate Pharmacy Manual. The diluted PHV01 vaccine and placebo will have similar appearance, ensuring blinding of study medication. It is anticipated that 1 mL of vaccine or placebo will be administered IM in the deltoid muscle using a 3-mL syringe with a 1.5-inch #23-gauge sterile needle. Prior to injection, the area to be injected will be prepped with an alcohol swab and allowed to dry before injection. While holding the needle at an approximate 90-degree angle to the skin, the needle will be directed through the skin, into the muscle of the deltoid. After injection, the needle will be disposed of into a rigid sharps container.

The study will enroll 36 subjects in a stepwise, dose ascension manner in 4 distinct Groups (Table 1) organized as 4 dosing Cohorts (Figure 1). Randomization will be stratified to ensure balance across the treatment groups with regards to gender. Different block sizes may be used.

Table 1: Dosage Regimen by Treatment Group

Treatment Group	Subjects	Test Article	PHV01 Dose (pfu & volume)	Route	Schedule
Group A	10	PHV01	1×10^5 pfu in 1 mL	IM	Day 1
Group B	10	PHV01	1×10^6 pfu in 1 mL	IM	Day 1

[figure not shown]
Group C	10	PHV01	1×10^7 pfu in 1 mL	IM	Day 1
Group D	6	Lactated Ringer's	1 mL	IM	Day 1

Abbreviations: IM = intramuscular; pfu = plaque forming units.

Subjects will be enrolled stepwise with safety reviews conducted between Dosing Cohorts to approve dosing the remaining subjects within that cohort and dose-escalation into the next Dosing Cohort (Figure 1).

Dosing Cohort #1 consists of Pioneer Group A (3 vaccinees at 1x10⁵ pfu and 1 placebo). *Note: As this is a FIH study, a maximum of 2 randomized subjects will be dosed per day in Cohort #1.* The Study Review Committee (SRC) (PI, Medical Monitor, and Sponsor's Chief Medical Officer) will review safety data through day 8, and if no pausing or stopping rules are met, will enroll Dosing Cohort #2, consisting of Remainder of Group (ROG) A (7 vaccinees at 1x10⁵ pfu and 1 placebo), and Pioneer Group B (3 vaccinees at 1x10⁶ pfu and 1 placebo). The SRC will review safety data through day 8 and, if no pausing or halting rules are met, will enroll subsequent Dosing Cohorts #3 and #4 in the same stepwise review and authorization process, to proceed to complete planned enrollment of all 36 subjects.

Figure 1. Flow Diagram for Dosing Cohorts and SRC Decision Points

- 36 subjects
- Screening Dec2023-Mar2024, Dosing on day 1 with F/U @ 6h, then day 2, 4, 8, 15, 29, 85, 181
- Dosing multiple people on a single day is preferred but not required. Single blind (subjects & site personnel)

v-vaccine; p-placebo

1.7. COMPLIANCE STATEMENT

The study will be conducted according to the protocol and in compliance with International Conference on Harmonisation (ICH) Good Clinical Practice (GCP). All identified study personnel will be trained to perform their roles and will carry out their responsibilities in accordance with ICH GCP guidelines.

1.8. STUDY POPULATION

The study will enroll and dose a total cohort of 36 healthy male and non-pregnant, non-lactating, adult female subjects, 18 to 60 years of age at the time of screening (inclusive). To avoid difficulties in interpretation, subjects are excluded if there is a history of a confirmed or suspected immunosuppressive or immunodeficient condition, including HIV-1 or HIV-2 infection, history of long COVID (35), cytotoxic therapy in the previous 5 years, and/or diabetes.

See Section 4.4 & 4.5 for inclusion and exclusion criteria. Refer to Section 7.1 for a statistical justification of the sample size.

^{*}Titer determined on release of drug product and will be $\geq 1 \times 10^7$ pfu/mL

1.9. SUBJECT IDENTIFIER CODE

In agreement with cGCP, each subject will be unambiguously identified by a code that allows the identification of all data reported for that subject.

Once the subject has provided informed consent at the screening visit, a unique subject screening number will be allocated.

Upon meeting all inclusion and no exclusion criteria, subjects will be deemed eligible for randomization into the study. Immediately prior to randomization, subjects will be assigned a unique treatment identification (randomization) number.

If for any reason after signing the ICF the subject fails to be randomized and dosed, the reason for not being dosed must be documented.

Once assigned, the subject, screening, and randomization number, cannot be reused. The Investigator must keep track of the names of the subjects enrolled and their identifying numbers in a Subject Identification Code List.

2. STUDY OBJECTIVES

2.1. PRIMARY SAFETY OBJECTIVE

To evaluate the safety and tolerability of the Marburg vaccine candidate, PHV01, when administered at graded doses (1×10^5 , 1×10^6 , 1×10^7 pfu/mL) given by the IM route in 1 mL to healthy adults.

2.2. PRIMARY IMMUNOLOGIC OBJECTIVES

To evaluate Marburg-specific IgG ELISA antibody and neutralizing antibody responses to graded doses of PHV01 given by the IM route to healthy adults.

2.3. SECONDARY OBJECTIVES

To evaluate vaccine viremia and shedding in saliva and urine after administration of PHV01.

2.4. EXPLORATORY OBJECTIVES

To obtain and preserve serum, blood, and peripheral blood mononuclear cell specimens for assays designed to dissect immunological mechanisms of protection and gene activation.

3. STUDY DESIGN

3.1. STUDY ENDPOINTS

3.1.1. Primary Safety Endpoints

- Incidence and severity of solicited injection site AEs (arm pain, local tenderness, erythema (redness), induration (swelling/firmness) and systemic AEs (objective fever, subjective fever, chills, sweats, headache, myalgia, arthralgia, fatigue, nausea, vomiting) and neurological AEs (blurry vision, changes in balance or coordination, confusion, disorientation, dizziness, severe headache, shaking or body tremors, slurred speech, tingling or numbness, weakness or feeling weak) between days 1 and 8, and days 9-15 after vaccination, per treatment group (active vaccination versus placebo) and stratified by relatedness.
- Incidence and severity of unsolicited AEs between days 1-8, days 9-15, and up to day 29 after vaccination, per treatment group (active vaccination versus placebo) and stratified by relatedness.
- Incidence and severity of arthritis and skin/mucosal lesions up to day 29 after vaccination using standard case definitions and stratified by relatedness. This includes where possible quantitative reverse transcription polymerase chain reaction (RT-qPCR) for detection of PHV01 and lesion biopsy for histopathology.
- Incidence of SAEs observed up to day 181 and stratified by relatedness.
- Incidence and severity of MAAEs observed up to day 181 and stratified by relatedness.
- Physical and neurological examination results, vital signs, normal and abnormal clinical laboratory values (hematology and clinical chemistry, urinalysis).
- Incidence of adverse events of special interest (AESIs), to include pneumonitis, acute respiratory distress syndrome, multiorgan failure, a hemorrhagic diathesis, certain neurologic events (encephalitis, myelitis, aseptic meningitis, optic neuritis, transverse myelitis, generalized convulsions, Guillain-Barré Syndrome, acute disseminated encephalomyelitis), thrombocytopenia, anaphylaxis, and vasculitides.

3.1.2. Secondary Safety Endpoints

- PHV01 in blood on days 1 (at 0 and 6 hours), 2, 4, 8, 15, and 29, as detected by quantitative reverse transcription polymerase chain reaction (RT-qPCR)
 - o Proportion of subjects with viremia detected by RT-qPCR
 - o Median duration of viremia, determined by RT-qPCR
 - o Geometric mean level of viremia, geometric mean peak level of viremia, and area under the curve (AUC)
- PHV01 in urine, saliva, biopsy, joint fluid, vesicle fluid, or swab of other suspect lesions on days 1 (at 0 and 6 hours), 2, 4, 8, 15, and 29, as detected by RT-qPCR
 - o Proportion of subjects with PHV01 detected by RT-qPCR
 - o Median duration of PHV01, determined by RT-qPCR

o Geometric mean copy number of PHV01, geometric mean peak copy number of PHV01, and area under the curve (AUC)

3.1.3. Safety Endpoint Collection

Safety will be assessed by analysis of the occurrence of TEAE and vaccinemia, as well as by adverse changes in laboratory evaluations (chemistry, hematology, urinalysis), vital signs, and physical including neurologic examinations. All AEs will be collected systematically through day 29 (Section 1.5.1). SAEs, MAAEs, and AESIs will be collected for the entire period each participant is on study with the help of Memory Aides, reviewed at the day 29, 85, and 181 visits.

AEs will be coded according to Medical Dictionary of Regulatory Activities (MedDRA) Version 26.1 (or latest) (36). A TEAE is defined as an AE that starts or worsens on or after the date and time of the study vaccination. AE endpoints include:

• Solicited TEAEs.

- O Solicited local AEs (at the injection site) are reported daily through day 14 and systemic reactogenicity symptoms, facilitated through the use of a memory aid, occurring from vaccination through 15 days following vaccination. *Note: solicited AEs for days 16-29 are limited to instances of neurological signs and symptoms, arthritis, and rash.*
- o Local reactogenicity signs and symptoms, including arm pain, local tenderness, erythema (redness), and induration (swelling/firmness).
- O Systemic reactogenicity signs and symptoms, including subjective and objective fever, shivering/chills, sweats, myalgia (generalized muscle aches), arthralgia (joint aches/pain, general or while moving joints; affected joints will be captured), joint swelling, joint tenderness, fatigue, gastrointestinal symptoms (nausea, vomiting, abdominal pain, and diarrhea), mucosal lesion (any sores or lesions, including mouth ulcers), skin lesion (including any rashes or blisters), and neurological symptoms (blurry vision, changes in balance or coordination, confusion, disorientation, dizziness, severe headache, shaking or body tremors, slurred speech, tingling or numbness, weakness or feeling weak). As noted in this paragraph, a severe headache is an adverse event that may represent a potential neurologic AESI.
- Solicited joint-related (joint aches/pain, joint swelling, and joint tenderness), mucosal lesion, and skin lesion TEAEs will be collected from vaccination through day 29, facilitated through the use of a Memory Aid. TEAEs will be recorded on the Memory Aids throughout the remainder of the study. Enhanced evaluation of arthritis and rash TEAEs will be done if the subject triggers protocol-specified algorithm and/or is referred to rheumatologist or dermatologist.
- Unsolicited TEAEs will be similarly collected from vaccination through day 29 with the use of a Memory Aid, and throughout the remainder of the study.

All TEAEs and clinical laboratory evaluations, including a standard metabolic chemistry panel, CBC, prothrombin time, activated partial thromboplastin time, and fever will be graded according to the toxicity grading scales (APPENDIX 1), which are based on the FDA document "Guidance for Industry: Toxicity Grading Scale for Healthy Adult and Adolescent Volunteers Enrolled in Preventive Vaccine Clinical Trials" (Sept 2007) (37). Vaccinemia is defined as a blood specimen

polymerase chain reaction (PCR) positive for rVSV (i.e., a detectable result \geq LLOQ genome copies(gc)/mL).

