7.5.1. Analysis Addressing the Primary Study Objective (Safety)

Solicited symptoms occurring during the 28 days following vaccination will be summarized by treatment group and by relatedness. The incidence and severity of solicited AEs to the vaccine over the 28-day follow-up period will be calculated. Presentations will include the number and percentage of subjects with at least 1 local AE, and at least 1 general (systemic) AE, as well as the incidence of each AE individually.

The number of subjects with at least 1 incidence of an unsolicited AE reported up to 28 days after vaccination will also be summarized overall and by treatment group. The severity and temporal relationship of the unsolicited AEs to vaccination will also be assessed. Presentations will also summarize unsolicited AEs by grade and vaccine-relatedness. Serious AEs occurring at any point during the trial will be summarized and relatedness to vaccine will be assessed. The incidence rate of solicited AEs may be compared between each treatment group and placebo using Fisher's exact test and logistic regression.

The level of vaccinemia (on days 1 [at 0 and 6 hours], 2, 4, 8, 15, and 29) and shedding will be assessed on all subjects. The proportion of subjects with detected vaccinemia, as well as the geometric mean and AUC of vaccinemia level, will be presented at each time point where data are collected. The relationship between vaccinemia level and dose will be explored in a mixed model for repeated measures (MMRM) analysis that incorporates dose level, time, and other potential predictive factors. A similar model will be used to explore the relationship between dose and the AUC of the vaccinemia level.

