4.4.3. Vaccine Viremia

The level of vaccine viremia and shedding will be assessed for all subjects by RT-qPCR in blood, urine, and saliva. For RT-qPCR results reported as < LLOQ, the result will be assigned a value of LLOQ/2 at such visit for computations. For RT-qPCR results reported as < LOD, the result will be assigned a value of 1 genome copies/mL for computations.

Vaccine viremia duration is defined as the time from first administration of study vaccine to vaccine viremia clearance detected by RT-qPCR. Subjects without vaccine viremia clearance will be censored at the last evaluable assessment.

The distribution for vaccine viremia duration by treatment group will be estimated by Kaplan-Meier methodology and the 25th percentile, median, 75th percentile, number and percentage of events and censored observations, and appropriate 95% CIs will be presented. If the 95% CIs of

three PHV01 groups overlap then the analysis will be repeated comparing the combined PHV01 group with the placebo group. The corresponding Kaplan-Meier curves will also be generated.

The proportion of subjects with vaccine viremia in blood, urine, and saliva, as well as the geometric mean of vaccine viremia level and the geometric mean of peak level, will be presented on Day 1 (at 0 and 6 hours), 2, 4, 8, 15, and 29 by specimen type, dose level and the combined PHV01 group.

Reverse cumulative distribution curves of rVSV RNA copies by specimen type will be generated by treatment group on Day 1 (at 0 and 6 hours), 2, 4, 8, 15, and 29, respectively, where the x-axis will be the observed log-10 transformed titers and the y-axis will be the percentage of subjects having a log-10 transformed titer greater than or equal to each of the observed log-10 transformed titers on the x-axis.

Line plots will present number of rVSV RNA copies by specimen type at each visit by treatment group.

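### Blood vaccinemia is scored positive only at or above LLOQ, although the endpoint is virus detected and the SAP carries detected sub-LLOQ results into level and AUC; urine and saliva have no stated cut

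*Protocol*

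**What the plan says.** **Endpoints.** Protocol 3.1.2 lists, for blood, "Proportion of subjects with viremia detected by RT-qPCR" and, for urine, saliva and lesion samples, "Proportion of subjects with PHV01 detected by RT-qPCR". SAP 1.2.5.1 repeats both. The analysis text in Protocol 7.5.1 also speaks of detection: "The proportion of subjects with detected vaccinemia".

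**Positivity rule.** The only written rule is in Protocol 3.1.3. It applies to a blood specimen that is PCR "positive for rVSV (i.e., a detectable result" at or above LLOQ. It does not mention urine, saliva or lesion samples.

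**Low results.** SAP 4.4.3 has two lower categories. One is covered by this rule: "For RT-qPCR results reported as < LLOQ, the result will be assigned a value of LLOQ/2 at such visit for computations". The other, for anything the laboratory returns as under the LOD, substitutes a single copy per mL.

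SAP 4.4.4 computes AUC on log10 copies and refers back to 4.4.3 for the geometric mean AUC.

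**Duration.** "Vaccine viremia duration is defined as the time from first administration of study vaccine to vaccine viremia clearance detected by RT-qPCR". No threshold for clearance is given.

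**Where the SAP is silent.** SAP 4.4.3 calls for the proportion with viremia in blood, urine and saliva by visit, but neither restates nor replaces the Protocol's LLOQ cut. SAP 8.1 says the handling of low results was revised on the basis of two memos, which are not among the documents.

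**The concern.** A separate category below LOD implies that a result reported as below LLOQ, but not below LOD, was detected without being quantifiable. The SAP does not use those words; this is the natural reading of two categories with two different substituted values. Under Protocol 3.1.3 such a blood sample is not vaccinemia, although the endpoint is named as detection.

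Two consequences follow. The proportion table for blood may report fewer subjects with virus than were detected, which is the less cautious direction for a live replicating vaccine in a first-in-human trial. And the proportion table can show no vaccinemia at a visit where the level and AUC tables show a signal from the same samples.

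The Protocol also uses the looser sense elsewhere. In Protocol 1.1.3.1, spinal cord RNA below LLOQ in the primate study is reported as found, and animals with it are called positive.

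**Working it through.** No figure in the plan depends on the vaccinemia cut, so there is none to reproduce. As a check of the interval method, the exact upper limit for 0/10 is 1 − 0.025^(1/10) = 30.85%, against 30.9% in Protocol 7.1.

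**1. One blood sample, side by side**

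| Result | Proportion (Protocol 3.1.3) | Value used (SAP 4.4.3) | log10 value |
|---|---|---|---|
| below LOD | negative | 1 | 0 |
| LOD to below LLOQ | negative | LLOQ/2 | log10(LLOQ/2) |
| exactly LLOQ | positive | LLOQ | log10(LLOQ) |

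The last step adds log10(2) = 0.30. The first adds log10(LLOQ/2), which is 1.0 for an assumed LLOQ of 20 copies/mL and 2.7 for 1000. So the level summary places the middle sample much nearer to the positive one than to the undetected one.

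**2. AUC**

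Sampling times in days since dosing are 0, 0.25, 1, 3 and 7 (to Day 8). Take a subject below LOD at 0 h and 6 h, detected below LLOQ on Days 2 and 4, and below LOD on Day 8. With L = log10(LLOQ/2), the trapezoid rule gives

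(0.75 × L/2) + (2 × L) + (4 × L/2) = 0.375L + 2L + 2L = 4.375L.

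The comparison subject, exactly at LLOQ on the same two days, has 4.375 × log10(LLOQ).

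| Assumed LLOQ | Detected below LLOQ | At LLOQ | Ratio |
|---|---|---|---|
| 20 | 4.38 | 5.69 | 77% |
| 100 | 7.43 | 8.75 | 85% |
| 1000 | 11.81 | 13.12 | 90% |

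The first subject has no vaccinemia at any visit under Protocol 3.1.3; the second does. A subject below LOD throughout has AUC 0. (The formula as it appears in SAP 4.4.4 has a minus sign between successive values. I used the trapezoid rule that the section names.)

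**3. Proportion in a dose group of 10**

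These are bounding cases, not predictions, with exact 95% intervals.
- All 10 detected below LLOQ: 0/10 (0 to 30.9%) by the LLOQ rule; 10/10 (69.2 to 100%) by detection.
- Five detected below LLOQ, the rest below LOD: 0/10 against 5/10 (18.7 to 81.3%).

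The geometric mean is the same under either rule: LLOQ/2 in the first case.

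**4. Share of subjects affected**

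Assume a subject's peak log10 copies is normal with SD 1. The share detected but scored negative is P(LOD ≤ peak < LLOQ).

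| Mean peak relative to LLOQ | LOD = LLOQ/3 | LOD = LLOQ/10 |
|---|---|---|
| 1 log below | 14% | 34% |
| at LLOQ | 18% | 34% |
| 1 log above | 9% | 14% |
| 2 logs above | 1.6% | 2.1% |
| 3 logs above | about 0.1% | about 0.1% |

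The answer runs from about a third of subjects to almost none, and the documents do not place the trial on this table.

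**5. Duration**

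Take clearance as the first sample below the cut. A subject quantifiable on Day 2, detected below LLOQ on Day 4 and below LOD on Day 8 clears at 3 days if the cut is LLOQ and at 7 days if it is LOD. The SAP does not say which applies.

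**The case against.** The strongest reply is that nothing here is contradictory. Protocol 3.1.3 says what counts as a positive in blood, and the endpoint can be read with that definition. LLOQ is a defensible cut, since low-copy PCR signals are less reliable. A geometric mean has no positive or negative status, and the substituted values exist only so that it can be computed. SAP 3.10 follows the same pattern for antibody, where a titer below LLOQ is called negative and set to LLOQ/2. That stands as a defence of LLOQ as a choice. It does not make a quantifiable proportion answer an endpoint worded as detection.

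A second reply is that the information is already shown. SAP 4.4.3 plans reverse cumulative curves by specimen and visit, whose height at log10(LLOQ/2) is the proportion not below LOD, and SAP 4.4.5 tabulates and lists PCR results. This is partly right. The curves show detection visit by visit, but not the proportion of subjects ever detected, nor duration.

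Third, one of the memos cited in SAP 8.1 may define positivity. If so, the rule still belongs in the SAP.

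A reader might also infer that shedding is understated. The documents do not support that: the LLOQ rule is written for blood alone, and urine and saliva have no stated cut. SAP 4.4.3 does use the viremia label for all three specimens, so the blood rule could be carried over in programming, but nothing says that it will be.

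Finally, the consequence is bounded. These are descriptive secondary endpoints. The pausing and halting rules (Protocol 3.7.2) do not use PCR results, and the contact precautions (Protocol 5.3) run for fixed periods.

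**Conclusion.** The point holds for blood as a mismatch of definitions: the endpoint is detection, the written rule is quantification, and the SAP carries detected sub-LLOQ samples into level and AUC. The proportion detected in blood can be understated, by an amount that cannot be stated without LOD, LLOQ and expected peaks. It is near zero if peaks are well above LLOQ. It would be tempting to say that one to three subjects in each group of 10 are miscounted, but that requires peaks within about one log of LLOQ, and nothing in the documents puts them there.

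For urine and saliva the defect is an absent threshold, and for duration an undefined clearance cut. The conclusion rests on reading a result below LLOQ but not below LOD as detected, and on the cited memos not settling the rule.

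**What to change.** In SAP 4.4.3, for blood, urine and saliva:
- report the proportion detected (at or above LOD) and, beside it, the proportion quantifiable (at or above LLOQ), per subject and per visit;
- state which of the two thresholds defines clearance in the Kaplan-Meier analysis of duration.

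Reconcile the vaccinemia definition in Protocol 3.1.3 with this, so that the Protocol and SAP do not conflict. Reporting both proportions avoids having to prefer one cut.

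The cost is a few extra table rows and a definition change in the Protocol, with no new samples or assays. Reported proportions may be slightly higher, and some low-level results will be of uncertain specificity. The trial can check the latter: with complete sampling, each of blood, urine and saliva has 36 pre-dose samples and 6 placebo subjects × 6 post-dose times = 36 more, 72 in all, in which vaccine RNA is not expected.
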